# 3.4 Safety Endpoint(s)

Safety evaluations include the following:

- AE, Adverse event
- SAE, serious adverse event
- Deaths
- ECG, electrocardiogram variables
- Vital signs, clinical laboratory testing (hematology and clinical chemistry)
- Transfusion requirement for PRBC and platelets

# 3.5 Additional Endpoint(s)

- Biomarker endpoints as follows:
  - Change in Variant Allele Frequency
- Pharmacokinetic (PK) endpoints for navitoclax and ruxolitinib are as follows:
  - 1. Cmax, maximum observed plasma concentration

- 2.  $T_{max}$ , the time to  $C_{max}$
- 3. AUCt, the area under the plasma concentration-time curve (AUC) from time 0 to the time of the last measurable concentration
- 4. β, the terminal phase elimination rate constant, only for navitoclax if the data warrants
- 5. AUC $_{\infty}$ , Area under the plasma concentration-time curve from time 0 to infinite time, only for navitoclax if the data warrants

Additional exploratory biomarker and PK endpoints may be evaluated (if required) and these will be analyzed without specifying in this study SAP.

# 4.0 Analysis Populations

[figure not shown]
In this study, study treatment is navitoclax + ruxolitinib (Cohort 1a, 1b and 3) or navitoclax alone (Cohort 2). Unless otherwise noted, study drug refers to navitoclax and ruxolitinib for combination therapy (Cohort 1a, 1b, and 3); and navitoclax for mono therapy (Cohort 2). Cohort 1 refers to Cohort 1a and Cohort 1b together.

The following sets will be used for analyses:

Full Analysis Set (FAS) includes all enrolled subjects who received at least one dose of navitoclax. The FAS will be used for all demographic/baseline analyses. Unless otherwise specified, the FAS is also the analysis population for the primary and the secondary endpoints.

The Safety Analysis Set includes all enrolled subjects who received at least one dose of navitoclax. The safety analysis set will be used for all safety analyses, unless otherwise specified.

The pharmacokinetics (PK) analysis set includes all the enrolled subjects who received at least one dose of navitoclax and have at least one post-dose PK assay results. The PK set will be used for PK analyses.

# 5.0 Subject Disposition

The FAS will be used to summarize subject disposition by cohort. The total number of subjects who were treated will be summarized.

A summary of subject accountability will be provided where the number of subjects in each of the following categories will be summarized by cohort.

- Subjects who were treated with at least one dose of navitoclax
- Subjects who discontinued study drug- navitoclax (all reasons and primary reason)
- Subjects who discontinued study drug- ruxolitinib (all reasons and primary reason)

# 6.0 Study Drug Duration and Compliance

[figure not shown]
#### 6.1 General Considerations

Safety analysis set will be used for the analyses of study drug duration and compliance. Descriptive statistics (number of non-missing observations, mean, standard deviation, median, maximum, and minimum) will be provided for navitoclax and ruxolitinib, respectively, by Cohort, unless otherwise stated. Based on the dosing schedule, for Cohort 1 and 3, data from navitoclax and ruxolitinib will be separately summarized, and for Cohort 2 data from navitoclax will be summarized.

# 6.2 Duration of Study Drug

Duration of study drug is calculated for each subject by the following formula, for navitoclax and ruxolitinib, respectively:

Duration of study drug (days) =  $Date\ of\ the\ last\ dose\ of\ study\ drug\ -Date\ of\ the\ first\ dose\ of\ study\ drug+1.$ 

The duration of study drug will be categorized as some interval of time (e.g., every 28-day). The number and percentage of subjects in each interval will be summarized.

# 6.3 Subject-Years of Exposure

Subject-years of study drug exposure is calculated as below for navitoclax and ruxolitinib, respectively:

Subject-years of exposure (sub-yr) = 
$$\frac{\text{Sum of duration of study drug for all subjects (days)}}{365.25}$$

## 6.4 Dose intensity (DI) and Relative Dose Intensity (RDI)

An observed dose intensity (ODI) will be derived for each subject who receives the study drug based on how it was actually administered. A planned dose intensity (PDI) will also be derived based on the protocol-specified schedule of the study drug.

For ODI it is calculated as:

[figure not shown]
ODI = 
$$\frac{\text{Actual total dose}}{\text{Actual total duration of treatment exposure (days)}}$$

For PDI it is calculated as:

PDI 
$$=$$
  $\frac{\text{Planned total dose over protocol specified}}{\text{Actual total duration of treatment exposure (days)}}$ 

RDI is defined as: RDI =  $(ODI/PDI) \times 100\%$ .

The RDI will be summarized based on the study drug administration form in EDC. Ruxolitinib administered before the first dose of navitoclax is considered as prior study treatment therapy collected in the Study Cancer Prior Systemic Therapies (Myelofibrosis)

form in EDC for Cohort 1 (Cohorts 1a and 1b). Ruxolitinib administered after the last dose of navitoclax for Cohort 1 (Cohorts 1a and 1b) is considered as post-study treatment collected in Post Study Drug Systemic Therapies form in EDC.

The actual total duration of treatment exposure in the above equations is defined as the last dose date minus first dose date + 1 for navitoclax or ruxolitinib, respectively. Descriptive statistics will be presented for navitoclax (for all Cohorts) and ruxolitinib (for Cohort 3, Cohort 1a and Cohort 1b) respectively.

Number and percentage of subjects who have dose reductions or interruptions, will be summarized.

# 7.0 Demographics, Baseline Characteristics, Medical History, and Prior/Concomitant Medications

#### 7.1 General Considerations

[figure not shown]
Demographics, baseline/disease characteristics, medical history, and prior and concomitant medications will be performed on the FAS by Cohort.

#### Definition of First Date of and Last Date of Study Treatment

First date of study treatment is the date of the first dose of navitoclax. Last date of study treatment is the date of the last dose of navitoclax.

#### Definition of Baseline

In general, baseline value refers to the last non-missing measurement value collected up to the first date of study treatment, unless otherwise specified in Section 7.2.

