- Prior to study enrollment for subjects to be enrolled in Cohorts 1b and 3.

For any laboratory test value outside the reference range that the investigator considers clinically significant:

- The investigator may repeat the test to verify the out-of-range value.
- The investigator will follow the out-of-range value to a satisfactory clinical resolution.
- A laboratory test value that requires a subject to be discontinued from the study or requires a subject to receive treatment, meets protocol specific criteria (see Section 6.1.7 regarding toxicity management), and/or the investigator considers clinically significant will be recorded as an adverse event.

Chemistry and Hematology

Chemistry and hematology will be performed at the study visits outlined in Appendix C and as needed throughout the study. Additionally, hematology will be collected:

- Predose and 4 hours after the first dose of navitoclax on Day 1 and at 24-hours post-first-dose on Day 2,
- Prior to navitoclax dose increases, navitoclax reductions (if during a clinic visit) or re-initiation of navitoclax after interruption.
- Additional time points in Appendix C through the end of the study

Chemistry and hematology labs should always be performed on the same day a bone marrow sample is obtained.

Coagulation

Prothrombin time (PT) and activated partial thromboplastin time (aPTT) and International Normalized Ratio (INR) samples will be collected as outlined in Appendix C and as needed throughout the study.

Lipid Monitoring (Cohorts 1a, 1b or 3 only)

Treatment with ruxolitinib has been associated with increases in lipid parameters including total cholesterol, low-density lipoprotein (LDL), and triglycerides. Any clinically significant changes in lipid parameters should be monitored and treated according to institutional guidelines for the management of hyperlipidemia.

12-Lead Electrocardiogram (ECG)

A single 12-lead resting ECG will be obtained at Screening, Week 4 (Day 29), Treatment Completion Visit, and as clinically needed. In the event Week 4 or Treatment Completion visit ECG cannot be performed due to travel and other restrictions related to the COVID-19 pandemic, perform the 12-lead ECG at the next earliest feasible visit or arrange to have an alternative acceptable local facility perform the ECG for the subject.

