Unless otherwise noted in the SAP, all analyses will be performed separately for 3 sets by study treatment:

Set 1: This set consists subjects from Cohort 1a and 1b.

- Set 2: This set consists all subjects from Cohort 2.
- Set 3: This set consists all subjects from Cohort 3.

8.1.1 **Baseline Characteristics**

Unless otherwise stated, baseline for a given variable will be defined as the last nonmissing value for that variable obtained prior to the first dose of any component of study drug.

Continuous demographic data (e.g., age, height, and weight) will be summarized with means, standard deviation, minimum, maximum, and range. Categorical data (e.g., sex, race, etc.) will be summarized with frequencies and percentages.

Frequencies and percentages will be computed for medical history parameters.

8.1.2 **Pharmacokinetics**

Plasma concentrations of navitoclax, potential navitoclax metabolite(s), and ruxolitinib and their available pharmacokinetic parameter values will be tabulated for each subject and by visit. Summary statistics will be computed for each sampling time and each parameter.

8.2 **Efficacy Endpoints**

[figure not shown]
8.2.1 **Primary Efficacy Endpoint**

The primary endpoint is at least 35% reduction from baseline in spleen volume at Week 24 (SVR_{35W24}) as measured by MRI/CT.

8.2.2 **Secondary Efficacy Endpoints**

The secondary endpoints are:

At least 50% reduction in TSS at Week 24 from baseline as measured by MFSAF version 4.0

- The anemia response rate
- Change in the bone marrow fibrosis grade according to the European consensus grading system³⁵ (Appendix F)

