- j. MFSAF version 4.0 diary will be performed daily beginning at screening visit, pre-dose on Day 1 through Week 36 visit. For subjects enrolled in Cohorts 1b and 3 the screening period should be long enough to ensure at least 7 days to collect the daily MFSAF version 4.0 prior to Day 1.
- k. EORTC QLQ-C30 version 3, PROMIS Fatigue SF 7a and PGIC should be completed prior to any other clinical assessments and prior to dosing.
- 1. Females of childbearing potential must have a negative serum pregnancy test result at Screening, and a negative urine or serum pregnancy test at Study Day 1. Negative pregnancy test must be available prior to first dose. Where required by local regulatory authority, urine pregnancy tests will be performed for females of childbearing potential every 4 weeks after Week 24 through treatment completion.
- m. Hematology will be collected pre-dose and 4 hours after the first dose of navitoclax on Day 1; 24-hours post-first-dose on Day 2; additional timepoints indicated above in Table 6; and prior to navitoclax dose increases, reductions (if during a clinic visit), or re-initiation after interruption. Additional monitoring may also be required as per Section 6.1.7.1 and Section 6.1.7.2.
- n. Chemistry will be collected pre-dose on Day 1 Week 0
- o. Refer to Section 5.3.1.3 for sample matrix requirements for biomarker and optional exploratory research samples.
- p. Collected at Week 48 (D337) and Week 96 (D673).
- q. Cohort 1a only.
- r. Cohorts 1a and 3 only.

obbie Navitoclax (ABT-263) M16-109 Protocol Amendment 11

EudraCT 2017-001398-17

Table 6. Study Procedures – Navitoclax Alone or in Combination with Ruxolitinib (Continued)

- Collected at Week 36 (D253), 48(D337), 60 (D421), 72 (D505), and 96 (D673).
- Collected Weeks 48 (D337), 72 (D505), and 96 (D673) for Cohorts 1b and 2, and Weeks 48 (D337), 72 (D505), 96 (D673), 120 (D841), and 144 (D1009) for Cohort 3.
- Collected Week 48 (D337) for Cohorts 1b, 2 and 3.
- Collected Week 96 (D673) for Cohorts 1b, 2, and 3.

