#### 7.2.2 Baseline Hemoglobin Laboratory Value

For hemoglobin laboratory test the baseline value will be defined as follows:

For subjects who received PRBC transfusion (for any reason) within 4 Weeks on or before the first date of study treatment, the baseline value is the minimum value observed before the transfusion, and the last non-missing value on or prior to the first date of study treatment.

For subjects who do not receive PRBC transfusion within 4 weeks on or before the first date of study treatment, the baseline value is the last observed value on or before the first date of study treatment.

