#### 7.2.3 Baseline Renal Function

Baseline renal function will be classified based on the estimated creatinine clearance (CLcr) per Cockroft-Gault method, The last non-missing serum creatine value collected on or before the first date of study treatment will be used as baseline (assuming Day 1 collection is prior to dose as timestamp was not collected). The following table illustrates the classification for renal function:

Table 2. Renal Function Group Based on CLcr

Renal Function Group	CLcr (mL/min)
Normal	CLcr ≥ 90
Mild Impairment	$60 \le \text{CLcr} < 90$
Moderate Impairment	$30 \le \text{CLcr} < 60$
Severe Impairment	$15 \le \text{CLcr} < 30$

[figure not shown]

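### The SAP sets baseline by calendar date, so a platelet or hemoglobin value drawn 4 hours after the first navitoclax dose can be taken as baseline

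*SAP*

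**What the plan says.** The SAP's general rule, in section 7.1, is that "baseline value refers to the last non-missing measurement value collected up to the first date of study treatment". The same section fixes that date: "First date of study treatment is the date of the first dose of navitoclax". Hemoglobin has its own rule in 7.2.2. For subjects with no red cell transfusion in the preceding 4 weeks, "the baseline value is the last observed value on or before the first date of study treatment". For subjects who were transfused in that period, the baseline is a minimum taken over pre-transfusion values and the last value, and that last value is again bounded by date.

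The protocol bounds baseline by dose. Section 8.1.1 states that "baseline for a given variable will be defined as the last nonmissing value for that variable obtained prior to the first dose" of any study drug component. The Screening text in 5.3.1.1 agrees: a Day 1 repeat replaces the screening value only if it was taken before dosing.

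On Day 1 the protocol schedules hematology twice. Section 5.3.1.1 lists "Predose and 4 hours after the first dose of navitoclax on Day 1 and at 24-hours post-first-dose on Day 2", and footnote m to Table 6 in Appendix C repeats the requirement. Footnote n places Day 1 chemistry before the dose only.

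**The concern.** A calendar-date rule gives the same answer as a before-first-dose rule only when nothing is measured after dosing on that date. For hematology, every subject is scheduled to have such a measurement. Followed as written, the SAP can label an on-treatment platelet count or hemoglobin value as baseline, contrary to the protocol.

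Platelets are the marker for which this is most awkward. Protocol 6.1.7.1 describes a rapid effect of navitoclax on mature platelets, and thrombocytopenia is its main expected toxicity. Hemoglobin matters for another reason: its baseline feeds a secondary endpoint. In SAP 8.4.1.2 it decides whether a transfusion-independent subject counts in the anemia response analysis at all (below 10 g/dL) and the level from which a 2 g/dL rise is measured.

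**Working it through.** There is no stated figure to reproduce. The check sets the rules against the sampling schedule and then follows each output.

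**1. Which Day 1 value does the rule pick?**
- If the two Day 1 draws can be ordered by time, the last value dated on or before Day 1 is the 4-hour one. The rule then selects the on-drug value by schedule, not as an exception.
- If they cannot be ordered, last is undefined. Sections 7.1 and 7.2.2 give no tie-break, so the choice is arbitrary.
- If the phrase up to in 7.1 were read as excluding Day 1, the pre-dose Day 1 sample would be lost. That reading does not fit the SAP: 7.2.2, 7.2.3 and 7.2.4 all include Day 1.

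**2. Does another SAP sentence rescue hematology?**
- Section 7.2.3 covers creatinine by "assuming Day 1 collection is prior to dose as timestamp was not collected", and 7.2.4 makes a like assumption for bilirubin and AST. Both suit chemistry, which has only a pre-dose draw on Day 1. The SAP makes no such assumption for hematology, and it would be untrue of the 4-hour sample.
- Section 9.3.1 anchors the CTCAE shift-table baseline to the first dose and takes the lowest grade when a day has several values. That protects the platelet shift tables twice. It makes an exception for baseline hemoglobin and refers back to 7.2.2.

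**3. Which outputs are exposed?**

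| Output | SAP place | Exposed? |
|---|---|---|
| Baseline platelet and hemoglobin summaries | Tables 4 and 5 | Yes |
| Baseline box, platelets and hemoglobin | 9.3.2 | Yes |
| Hemoglobin shift table | 9.3.1, by exception | Yes |
| Anemia response, transfusion-independent subjects | 8.4.1.2 | Yes |
| Duration of anemia response, same subjects (start date) | 8.5.1.7, Table 6 | Yes |
| Platelet shift tables | 9.3.1 | Largely protected |
| Spleen volume response at Week 24 | 8.3.1 | Not materially |

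**4. How large could it be?** The documents give no 4-hour change in either variable, so these figures are illustrations under assumed changes.

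*Platelets* (× 10⁹/L): recorded baseline = pre-dose count × (1 − assumed fall).
- Pre-dose 160 with falls of 10%, 20% and 40%: 144, 128 and 96.
- Fall needed to leave the Table 4 category of at least 100: from 105, 1 − 100/105 = 4.8%; from 120, 1 − 100/120 = 16.7%.
- Fall needed to drop below 75 from 105: 1 − 75/105 = 28.6%.

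Cohorts 1a, 1b and 3 require at least 100 at screening, so such a subject would be tabulated below the entry limit although eligible.

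*Hemoglobin* (g/dL), transfusion-independent subject, assumed difference of 0.3 either way:
- Pre-dose 10.2 is outside the analysis. At 10.2 − 0.3 = 9.9 the subject enters it, with a response target of 11.9.
- Pre-dose 9.8 is in the analysis with a target of 11.8. At 9.8 + 0.3 = 10.1 the subject drops out; at 9.8 − 0.3 = 9.5 the target falls to 11.5.

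The denominator and the numerator of the anemia response rate can therefore both move, in either direction.

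**The case against.** The strongest reply is that this is loose wording rather than a chosen on-drug baseline. The SAP presents itself as elaborating the protocol, which calls for pre-dose values in two places. Sections 7.2.3, 7.2.4 and 9.3.1 all point to a pre-dose intention, and detail is left to a Statistical Programming Plan that is not among these documents. The 4-hour sample may never be used in practice. That is fair as to intent. It does not remove the need for a correction, because the rule as written produces the wrong value and nothing in the SAP tells the programmer to set the 4-hour draw aside.

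Some stronger readings are tempting, but the documents do not support them.
- *Hematology carries no timestamp.* The SAP's remark concerns creatinine. Whether hematology has a time or a time-point label is not stated.
- *Platelet toxicity will be understated against baseline.* The planned platelet comparison is the shift table, which is protected. The plots in 9.3.2 show values by visit, and no platelet change-from-baseline table is specified. What remains is one box per cohort and the descriptive baseline rows.
- *Anemia response will be inflated.* The protocol describes a rapid platelet effect but no 4-hour effect on hemoglobin. The error is real near the 10 g/dL limit and in the 2 g/dL target, but its direction is unknown.
- *A fall above 40% in 24 hours is expected.* In the protocol that figure triggers additional blood counts; it does not predict the usual fall. The documents place the nadir in the first few days of dosing.

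**Conclusion.** The point stands as a defect in a stated rule. SAP 7.1 and 7.2.2 allow a post-dose Day 1 platelet or hemoglobin value to serve as baseline, against protocol 8.1.1 and 5.3.1.1. That conclusion rests on the text alone. If the two draws can be ordered in time, the post-dose value is the one chosen; if not, the choice is undefined.

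The reach is limited to the exposed outputs listed above, of which anemia response is the most important because it is a secondary endpoint. The size cannot be determined from the documents, and the platelet and hemoglobin figures show only what assumed changes would do. The correction should be made, but the primary result does not depend on it.

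**What to change.** Amend SAP 7.1 and 7.2.2 as follows.
- Only values obtained before the first navitoclax dose are eligible as baseline.
- For hematology on Day 1, use the sample labelled pre-dose and never the 4-hour sample.
- If two Day 1 values cannot be told apart, use the last value before Day 1.
- Keep the minimum-value rule in 7.2.2 for subjects transfused within 4 weeks, applied to pre-dose values only. Replacing the whole section with a simple last-value rule would delete it and change the hemoglobin baseline used for anemia response.

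The cost is a sentence or two in the SAP and a filter in the programs. No additional data are needed, and no sample size or design figure changes.

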#### 7.2 Additional Baseline Definitions

#### 7.2.1 Baseline TSS Value

The total symptom score (TSS) will be measured by Myelofibrosis Symptom Assessment Form (MFSAF) v4.0. The daily TSS scores will be calculated by summing up scores from 7 items of the MFSAF. All seven items must be completed for a daily TSS score to be computed. The worst (highest) daily TSS score will be considered as the daily TSS for a day when multiple responses on the same day were reported.

For subjects who enrolled under Study Protocol Amendment 7 or earlier version, the baseline TSS will be calculated by averaging all available daily TSS score collected up to the first date of study treatment (including the first date of study treatment).

For subjects who enrolled under Study Protocol Amendment 8 or later version, the baseline TSS score is defined as the average of the daily TSS score within 7 days before the first date of study treatment (not including the first date of study treatment). At least 4 days of scores are required to calculate the baseline TSS score. If a subject does not have at least 4 days of scores before the first date of the study treatment (not including the first date of study treatment), the subject will not have a baseline TSS score (see detail in Appendix C).

#### 7.2.2 Baseline Hemoglobin Laboratory Value

For hemoglobin laboratory test the baseline value will be defined as follows:

For subjects who received PRBC transfusion (for any reason) within 4 Weeks on or before the first date of study treatment, the baseline value is the minimum value observed before the transfusion, and the last non-missing value on or prior to the first date of study treatment.

For subjects who do not receive PRBC transfusion within 4 weeks on or before the first date of study treatment, the baseline value is the last observed value on or before the first date of study treatment.

#### 7.2.3 Baseline Renal Function

Baseline renal function will be classified based on the estimated creatinine clearance (CLcr) per Cockroft-Gault method, The last non-missing serum creatine value collected on or before the first date of study treatment will be used as baseline (assuming Day 1 collection is prior to dose as timestamp was not collected). The following table illustrates the classification for renal function:

Table 2. Renal Function Group Based on CLcr

Renal Function Group	CLcr (mL/min)
Normal	CLcr ≥ 90
Mild Impairment	$60 \le \text{CLcr} < 90$
Moderate Impairment	$30 \le \text{CLcr} < 60$
Severe Impairment	$15 \le \text{CLcr} < 30$

[figure not shown]
